7.2.5.2 Vaccine immunogenicity

The immunogenicity of ETVAX[®] has previously been documented in Swedish adults in the OEV-121 study. The results showed that a full adult dose of ETEC vaccine administered together with 10 µg dmLT adjuvant resulted in 93% IgA and/or IgG seroconversion (≥ 2 -fold increase) against LT_B in samples collected 7 days after the second dose [12]. The vaccine also induced strong IgA responses against both LT_B and CFs in fecal samples and antibodies in lymphocyte supernatants (ALS) specimens, reflecting mucosal immune responses. Serum from immunized subjects also had strong LT toxin neutralization activity [12]. Serum

antibody responses against LTB also correlated significantly with LTB-specific mucosal responses measured in ALS specimens. dmLT adjuvant significantly enhanced ALS IgA responses to CS6, which is the antigen present in the lowest amount in the ETVAX vaccine, supporting the dose-sparing effect of dmLT previously observed in mice [10, 12].

In the OEV-122 study 100% of the adult Bangladeshi subjects receiving the vaccine alone or with 10 µg dmLT responded with an at least 2-fold response in anti-LTB IgA antibodies in both serum and ALS specimens [14]. ALS IgA responses to CFs were also observed in 100% of subjects. The high response is probably reflecting that in Bangladesh a high percentage of the population has experienced ETEC infections prior to vaccination.

Mucosal (ALS) as well as plasma IgA responses in Bangladeshi children 2-5 years were comparable to those in adults both in magnitude and frequencies [15]. Responses in children 1-2 years were also good with ALS IgA responses to all five antigens in a majority of vaccinees and somewhat lower frequencies in plasma. With regard to immune responses in the 6-11 months old infants immune responses to the CFs were lower than in the older age groups. Furthermore, response rates in the infant placebo recipients were considerably higher than in older children, probably due to very high frequencies of asymptomatic ETEC infections in this age group as previously shown in a birth cohort study in Bangladesh [17]. In spite of this, mucosal immune responses (ALS and/or fecal SIgA) were significantly higher against all vaccine antigens in the infant vaccinees than in the placebo recipients [15].

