In the OEV-123 study 81% of the Finnish vaccine recipients responded with at least a 2-fold increase in anti-LTB IgA serum antibodies after vaccination with ETEC vaccine + 10 µg dmLT.

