The vaccine will be administered orally twice to each subject at a target interval of 14 days. If the subject is unable to come for the third study visit on day 15 due to eg illness or rules regarding quarantine due to the COVID-19 epidemic, the second vaccine dose can be administered up to 28 days after the first dose. A prolonged interval between vaccine doses did not affect the serum responses to CTB component of the cholera vaccine Dukoral, which is highly homologous to LCTBA, when tested in Swedish volunteers [32]. Thus, serum CTB-specific IgA and IgA responses were comparable in both magnitude and frequency in subjects receiving Dukoral 14 days or 28-48 days apart, motivating the extended interval between doses in this ETEC vaccine trial compared to previous trials [32].

Many non-inferiority studies of parenteral vaccines use a 10% non-inferiority margin, but larger margins are also relatively common [33]. The 15% non-inferiority margin used in this non-inferiority study is motivated by the higher individual variability in vaccine responses and lower responder frequencies often observed with mucosal compared to parenteral vaccines. As an example, a comparison an oral inactivated *Shigella flexneri* 2 a vaccine gave a maximum serum response of 70% [34] as compared to a *S. flexneri* 2a conjugate given parentally, where 92-100% of the vaccinees responded in serum [35]. The response rate for the whole cell components of ETVAX[®] in serum is quite low (3-19% in a Western adult population respond after two doses of vaccine), whereas the mucosal immune responses are much stronger (71-97%) [12]. The response against the LCTBA protein is quite different resulting in a 79-90% seroconversion after two doses (OEV-123 CSR, [12]). Still, this is substantially lower than what is seen with many parenteral vaccines. Since no formal correlate of protection exists for ETEC or most other mucosal vaccines, the protective efficacy of the new formulation of the ETVAX[®] vaccine can only be supported by data from efficacy studies. If the new vaccine is found to be non-inferior to

the old vaccine in this study, this will support that it is reasonable both from an ethical and economical perspective to proceed to test the efficacy of this vaccine formulation in large Phase 3 trials in ETEC endemic areas.

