9.3 Selection of study population

9.3.1 Recruitment

The clinical part of the recruitment will be conducted by Clinical Trial Center (CTC) located at the Sahlgrenska University Hospital in Gothenburg, Sweden. This centre has helped recruiting the same category of volunteers, as will be recruited for the non-inferiority bridging study, for all previous studies of ETVAX® in Swedish adult volunteers [11, 12, 31].

Previous experience indicate that the number of recruited subjects should not be a problem, and the historical drop-out rate has been low (less than 5%) [12]. The compliance is also expected to be excellent, based on previous experience. However, due to the ongoing COVID-19 epidemic, a higher drop-out rate is expected (estimation 10%), since even mild symptoms may prevent study visits (See section 9.4.3)

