9.7.1.2 Medical/surgical history and concomitant medication

Medical/surgical history and prior/concomitant medications will be presented by descriptive statistics for each vaccination group.

9.7.1.3 Analysis of efficacy (Seroconversion rates of IgA and/or IgG anti-LTB antibodies in serum)

The primary endpoint, response, will be defined as “yes” for patients with at least a 2-fold increase in IgA and/or IgG antibody levels against LTB in serum between pre- and post-immunization samples (Visit 4 versus Visit 2).

The response rates (seroconversion rates) within treatment groups, p_{wet} and $p_{partially_dried}$, will be estimated as the proportion of responders (response = “yes”) in each treatment group. The primary analysis of the study seeks to compare the seroconversion rates using the difference

$$d = p_{partially_dried} - p_{wet}$$

The following non-inferiority hypothesis will be tested, using a -15% non-inferiority limit (on an absolute scale):

H_0 : The seroconversion rate of the partially dried group is lower than that of the wet group, $d < -0.15$

H_A : The seroconversion rate of the partially dried group is higher than or equal to that of the wet group, $d \geq -0.15$

A two-sided 95% confidence interval (CI) for d will be calculated by normal approximation. The lower limit of the CI will be compared to the non-inferiority limit -0.15. If the lower CI limit is larger than or equal to the non-inferiority limit, the null hypothesis will be rejected, and the result will be taken as supporting non-inferiority of the partially dried formulation compared to the wet formulation.

The normal approximation requires at least 5 patients in each cell of the Treatment by Vaccine response contingency table. If assumptions are not fulfilled, a non-parametric CI will be used instead.

The primary endpoint will be summarized for the full analysis set (FAS) and the per protocol analysis set (PPAS). The primary endpoint analysis of PPAS will be considered the primary analysis of the study.

The primary endpoint, i.e. the proportion of responders with at least a 2-fold increase in LTB-specific IgA and/or IgG antibody levels, will be summarized with descriptive statistics for the

PPAS and FAS. In addition, the proportion of responders with at least a 4-fold increase in IgA and/or IgG antibody levels will be presented. The levels of serum antibodies at visit 2 and visit 4 and the fold rise (magnitude of response) will also be presented for both IgA and IgG.

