9.7.4.3 Determination of sample size

Assuming a seroconversion rate of 85% in both the wet and the new formulation, and aiming to prove non-inferiority with margin -15% (on an absolute scale), 126 subjects are needed in each treatment arm to achieve 90% power. This calculation was done with Farrington-Manning's method, assuming that the study will be evaluated by a two-sided 95% confidence interval for the difference between the two treatment groups' seroconversion rates.

A 10% dropout rate is assumed. The target number of patients to be recruited per study arm is therefore **140**.

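### The primary non-inferiority interval is not named, although sizing used Farrington-Manning; read as Wald at 126 per arm, one-sided error is about 2.5-2.6% at 79-85% wet response but 2.8-3.0% at 90-93%

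*Combined protocol and SAP*

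**What the plan says.** Section 9.7.1.3 (Analysis of efficacy) defines d as the seroconversion rate on the partially dried formulation minus that on the wet formulation. A two-sided 95% interval for d "will be calculated by normal approximation. The lower limit of the CI will be compared to the non-inferiority limit" of -0.15, and non-inferiority is declared if the lower limit is at or above that value. A condition follows: "The normal approximation requires at least 5 patients in each cell of the Treatment by Vaccine response contingency table". So does a fallback: "If assumptions are not fulfilled, a non-parametric CI will be used instead". Neither the variance estimator nor the fallback method is named, and nothing is said about a continuity correction.

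Section 9.7.4.3 (and the synopsis) arrives at 126 per arm for 90% power, assuming 85% in both arms and a 15-point margin. "This calculation was done with Farrington-Manning's method", it states.

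The protocol gives several earlier response rates. Section 7.2.5.2 says that the full dose with 10 µg dmLT in Swedish adults "resulted in 93% IgA and/or IgG seroconversion" 7 days after the second dose. Section 9.2 describes the LCTBA response as "resulting in a 79-90% seroconversion after two doses". Section 7.2.5.2 also reports that "81% of the Finnish vaccine recipients responded with at least a 2-fold increase in anti-LTB IgA serum antibodies", which is IgA alone and not the composite.

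Section 9.7 promises a SAP that will follow the protocol's outline and add the remaining detail. The document reviewed contains no separate SAP text.

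**The concern.** The sample size comes from a named test, but the words describing the analysis do not identify that test. At least three rules fit them: an unrestricted Wald interval, a continuity-corrected Wald interval, and a score interval, which is also a large-sample normal method. The 5-per-cell condition points towards Wald without saying so.

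The rules differ in error and power. Wald uses the observed proportions for its standard error. When wet response is high and the true difference is at the margin, that standard error tends to be too small, and non-inferiority is declared too often. The high-response region is plausible here because the 93% is for the same endpoint, in the same kind of population and at the same sampling time. A continuity correction errs the other way and costs power. Leaving the choice open also leaves room to settle it after the data are known.

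**Working it through.** **Inputs.** Margin -0.15, two-sided 95% interval with the lower limit used, so one-sided 2.5% (9.7.1.3). 85% in both arms, 90% power, 126 per arm, 10% drop-out, 140 recruited (9.7.4.3). Wet rates: 79-90% (9.2), 81% IgA only and 93% composite (7.2.5.2). Historical drop-out below 5% (9.3.1).

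**Step 1: reproduce the sample size.** n = [1.96·√V0 + 1.2816·√V1]² / 0.15².
- V1 = 2 × 0.85 × 0.15 = 0.255.
- V0 uses the maximum-likelihood rates restricted to d = -0.15, which are 0.7489 (dried) and 0.8989 (wet): V0 = 0.7489 × 0.2511 + 0.8989 × 0.1011 ≈ 0.279.
- Result: n = 125.8, hence 126; 126/0.9 = 140. The plan's figures reproduce.
- With the unrestricted variance throughout, n = (1.96 + 1.2816)² × 0.255/0.0225 = 119.1, hence 120. So 126 is indeed a Farrington-Manning (FM) figure.

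**Step 2: exact one-sided error.** Enumerate every pair of binomial outcomes with the dried rate equal to the wet rate minus 0.15, and add the probabilities of pairs that declare non-inferiority.
- Wald: d − 1.96·√[p₁(1−p₁)/n₁ + p₂(1−p₂)/n₂] ≥ −0.15, with p₁, p₂ observed.
- FM: (d + 0.15)/SE ≥ 1.96, with SE from the restricted estimates.
- Continuity-corrected Wald: as Wald, with 0.5(1/n₁ + 1/n₂) also subtracted.

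At 126 per arm:

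| Wet rate | Wald | FM | Cell check triggered | Wald, every triggered case scored a failure |
|---|---|---|---|---|
| 79% | 2.52% | 2.52% | 0.0% | 2.52% |
| 81% | 2.53% | 2.53% | 0.0% | 2.53% |
| 85% | 2.57% | 2.52% | 0.0% | 2.57% |
| 90% | 2.82% | 2.49% | 0.4% | 2.82% |
| 93% | 3.01% | 2.41% | 5.5% | 3.00% |

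Up to 85% the departure from 2.5% is mostly binomial discreteness. The last column bounds what any fallback could achieve: none can bring the error back to 2.5%. The continuity-corrected rule has error 1.77-1.89% over 79-93%.

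**Step 3: power with 85% in both arms.** At 126 per arm: Wald 91.7%, FM 90.8%, continuity-corrected 88.4%. At 133 per arm (140 × 0.95): 92.8%, 92.2% and 90.2%.

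**Step 4: other arm sizes.** Error, Wald / FM:

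| Dried / wet | Wet 85% | Wet 90% | Wet 93% |
|---|---|---|---|
| 133 / 133 | 2.62 / 2.50% | 2.70 / 2.49% | 2.84 / 2.47% |
| 132 / 120 (assumed) | 2.42 / 2.42% | 2.68 / 2.56% | 2.85 / 2.46% |
| 120 / 132 (assumed) | 2.71 / 2.47% | 2.85 / 2.49% | 3.09 / 2.39% |

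**Step 5: which outcomes change.** At 126 per arm with at least 100 wet responders, 12 outcome pairs differ. In all 12 Wald passes and FM does not, and 7 do not trigger the cell check. Example: wet 117/126, dried 108/126, d = −9/126 = −0.0714.
- Wald: SE 0.0387, lower limit −0.0714 − 1.96 × 0.0387 = −0.147, pass.
- FM: restricted rates 0.797 and 0.947, SE 0.0410, (−0.0714 + 0.15)/0.0410 = 1.92, below 1.96; lower score limit −0.152, fail.

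If the arms are truly equal, the two rules disagree in 0.2-1.0% of trials at 79-93%. If both respond at 93%, the unnamed fallback would be needed in 10.7% of trials.

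**The case against.** Variance form, continuity correction and fallback are the kind of detail that Section 9.7 leaves to the SAP. A SAP naming a score interval need not contradict 9.7.1.3 and would match 9.7.4.3. That stands as a limit: what is shown is that the protocol text leaves the method open, not that the gap persists in a SAP not available here.

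The error figures are conditional on the Wald reading and are small. At the planning value of 85% the two rules differ by 0.05 points. Only the 93% rate reaches 3.0%, and it comes from one group of unstated size within a trial of 129 Swedish adults (7.3.2). With 133 per arm the 93% figure falls to 2.84%. All of this stands. It limits the size of the effect but does not make 90-93% implausible.

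Sizing with FM does no harm if Wald is used: the trial is then slightly over-sized. That is also right, and the sample size is not in dispute. The power loss under a continuity correction disappears if drop-out is near the historical rate (90.2% at 133 per arm).

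Finally, naming any single interval would close the specification gap. True, but naming Wald would leave the excess error at high response. FM removes it and agrees with the sizing.

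**Conclusion.** The concern holds. The protocol does not identify the interval for its only confirmatory test, nor the fallback. On the natural Wald reading at 126 evaluable per arm, false non-inferiority is 0.3-0.5 points above 2.5% at wet rates of 90-93% and close to nominal at 79-85%. The cell check cannot correct this. On the continuity-corrected reading, power is 88.4% where 90% was planned. These figures assume independent binomial outcomes and a true difference of -15 points for error; power assumes 85% in both arms. Few outcomes would change, but with at least 100 of 126 wet responders every change favours declaring non-inferiority. This is a modest point that should be fixed, and it casts no doubt on the 126 or the 140 per arm.

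**What to change.** In Section 9.7.1.3, and in the SAP, replace the normal approximation, the 5-per-cell condition and the non-parametric fallback with one named method for all outcomes: the two-sided 95% Farrington-Manning score interval. State the test explicitly. Compute the standard error from the maximum-likelihood rates restricted to d = −0.15, and declare non-inferiority if (observed d + 0.15)/SE is at least 1.96. This is the same as a lower score limit of at least −0.15. If the SAP already names this interval, only the protocol wording needs aligning. Either way, settle it before unblinding.

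The cost is one paragraph of text, with no change to 126 or 140 per arm. Against Wald, power with 85% in both arms falls from 91.7% to 90.8% at 126 per arm and from 92.8% to 92.2% at 133. If the per-protocol set shrank to 120 per arm, power would be 89.5% against 90.4% for Wald.

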9.7.2 Analysis of safety

9.7.2.1 Vital signs

Change from baseline in vital signs (blood pressure, heart rate and body temperature) will be presented by individual time courses for each parameter and subject and summarized by dose group.

9.7.2.2 Adverse Events (AEs)

AEs and SAEs will be recorded from the start of IMP administration until the Follow-up Visit. AEs that occur before first treatment with IMP will be reported separately as baseline event.

All AEs will be described in terms of the treatment/dose at which they occurred. AEs will be coded using the Medical Dictionary for Regulatory Activities (MedDRA) and summarized by Preferred Term (PT) and System Organ Class (SOC). The number of subjects reporting AEs, and the number of AEs reported will be presented by dose group. The events will be tabulated by SOC, PT and by severity and relationship to IMP. SAEs will also be presented in separate tabulations. The number of subjects experiencing an AE in connection to each treatment will be presented.

9.7.3 Analysis of exploratory assessment

The exploratory assessments will be reported separately from the Clinical Study Report (CSR). The exploratory assessments may continue after unblinding of the main study.

Results from exploratory analyses will be summarized using descriptive statistics. The following parameters will be included: for categorical variables, the number and percent in each category; for continuous variables, median (with quartiles), range (minimum, maximum), and geometric means. Magnitudes (fold-rises) of serum antibodies (against LTB measured by ECL and against additional bacterial antigens), memory B cell, antibody secreting cell and T cell responses will be determined at each time point post vaccination compared to pre vaccination. Frequencies of subjects responding with ≥ 2 -fold increased levels of antibodies and markers reflecting T cell activity post vaccination compared to pre vaccination will be determined. Assessment of the change from the baseline measurement to a follow-up measurement will be analyzed using the Wilcoxon signed-ranks test, with adjustment for multiple testing using the Holm's method, when applicable. Correlations between different types of responses will be analyzed using the Spearman test. P values < 0.05 will be considered to be statistically significant.

9.7.4 Analysis data sets

9.7.4.1 Full Analysis Set (FAS)

Unless otherwise stated, statistical evaluations will be based on all subjects who have received randomized treatment with IMP and have available data. Evaluations will be done according to actual treatment received regardless of treatment assigned at randomization. A treatment group will consist of all subjects treated with a specific formulation. The FAS data set will be used for the safety and tolerability assessments as well as for the efficacy endpoints.

9.7.4.2 Per Protocol Analysis Set (PPAS)

The PPAS comprises data from all subjects randomized and treated with evaluable efficacy data, and no major protocol deviation that significantly affects the evaluability of the subject in the study. The PPAS will be used for presentation of the primary endpoint.

9.7.4.3 Determination of sample size

Assuming a seroconversion rate of 85% in both the wet and the new formulation, and aiming to prove non-inferiority with margin -15% (on an absolute scale), 126 subjects are needed in each treatment arm to achieve 90% power. This calculation was done with Farrington-Manning's method, assuming that the study will be evaluated by a two-sided 95% confidence interval for the difference between the two treatment groups' seroconversion rates.

A 10% dropout rate is assumed. The target number of patients to be recruited per study arm is therefore **140**.

9.7.5 Statistical/analytical issues

9.7.5.1 Adjustments for covariates

No adjustment for covariates in statistical analyses are planned, as the study is randomized and double-blinded.

9.7.5.2 Handling of dropouts or missing data

The handling of dropouts and missing data will be provided in the SAP.

9.7.5.3 Multi-centre studies

The study will be conducted at one site.

9.7.5.4 Multiple comparison/multiplicity

Only a single primary hypothesis test will be performed, giving no need for multiple testing adjustment. All other tests will be considered descriptive and should be interpreted with caution. Exploratory statistical tests will be adjusted for multiple testing by Holm's method.

9.7.5.5 Active-control studies intended to show equivalence

Not applicable

9.7.5.6 Examination of subgroups

No examination of subgroups is planned

9.7.5.7 Interim analyses and data monitoring

There will be no interim analysis, internal Safety Review Committee or Data Monitoring Committee for this study.

9.8 Data Management

Data management based on GCP refers to the activities defined to achieve safe routines to efficiently enter subject information into a database, avoiding errors.

The data management activities, such as procedures of validating data entered in the e-CRF, will be described in a separate data management plan. The e-CRF will be designed in accordance with the Clinical Study Protocol.

9.8.1 The web based e-CRF

Clinical data (including AEs and concomitant medications) will be entered into a 21 CFR Part 11-compliant e-CRF [REDACTED] provided by [REDACTED]. The e-CRF includes password protection with 2-Factor Authentication and internal quality checks, such as automatic range checks, to identify data that appear inconsistent, incomplete, or inaccurate. Clinical data will be entered directly from the source documents, which are to be defined at the site before inclusion of the first subject.

Authorised study site personnel designated by the Investigator will complete data collection. Appropriate training will be completed with the Investigator and all authorised study site personnel prior to any data being entered into the system for any study subject. Each user will have a personal and unique account. E-CRF data entries will be attributable to the unique user.

Captured data will be monitored electronically. Source data verification (SDV) and source data review will be performed at the site as described in the monitoring guidelines.

9.8.2 Entering of data into the e-CRF

All data must be entered in English.

The e-CRFs should always reflect the latest observations made during the subject's participation in the study. The e-CRFs should be completed as soon as possible during or after the subject's visit.

If some assessments are not done, or if certain information is not available, not applicable or unknown, this will be indicated in the e-CRF.

Entries triggering internal e-CRF checks will be presented as errors and warnings. Forms with incomplete entries or that contains triggered errors cannot be set to completed state.

The Investigator must verify that all data entries in the CRFs are accurate and correct by signing the completed CRF.

Once all data have been entered, verified, and validated, the database will be locked.

After the e-CRF has been locked, the data will be sent to the Sponsor and a copy to the research clinic to be filed in the Investigator Study File (ISF) for archiving.

